## Abbreviations

AE	Adverse Event
AF	Atrial Fibrillation
ANCOVA	Analysis of Covariance
CFR	Code of Federal Regulations
CLIA	Clinical Laboratory Improvement Amendments
CT	Computed Tomography
MP	Monitoring Plan
COC	Certificate of Confidentiality
CONSORT	Consolidated Standards of Reporting Trials
CRF	Case Report Form
DCC	Data Coordinating Center
DHHS	Department of Health and Human Services
DSMB	Data Safety Monitoring Board
DRE	Disease-Related Event
EC	Ethics Committee
eCRF	Electronic Case Report Forms
FDA	Food and Drug Administration
FDAAA	Food and Drug Administration Amendments Act of 2007
FFR	Federal Financial Report
GCP	Good Clinical Practice
GLP	Good Laboratory Practices
GMP	Good Manufacturing Practices
GP	Ganglionated Plexus
GWAS	Genome-Wide Association Studies
HFS	High Frequency Stimulation
HIPAA	Health Insurance Portability and Accountability Act
IB	Investigator's Brochure
ICH	International Conference on Harmonization
ICMJE	International Committee of Medical Journal Editors
IDE	Investigational Device Exemption

IND	Investigational New Drug Application
IRB	Institutional Review Board
ISM	Independent Safety Monitor
ISO	International Organization for Standardization
ITT	Intention-To-Treat
LSMEANS	Least-Squares Means
MedDRA	Medical Dictionary for Regulatory Activities
MOP	Manual of Procedures
MSDS	Material Safety Data Sheet
NCT	National Clinical Trial
NIH	National Institutes of Health
NIH IC	NIH Institute or Center
OHRP	Office for Human Research Protections
PI	Principal Investigator
QA	Quality Assurance
QC	Quality Control
SAE	Serious Adverse Event
SAP	Statistical Analysis Plan
DSMC	Data Safety Monitoring Committee
SoA	Schedule of Activities
SOC	System Organ Class
SOP	Standard Operating Procedure
UADE	Unanticipated Adverse Device Effect
UP	Unanticipated Problem
US	United States

## 1 STUDY SUMMARY

### 1.1 Synopsis

**Title:** PROSPECTIVE EVALUATION OF COMPUTED TOMOGRAPHY GUIDED MAPPING AND ABLATION OF CARDIAC GANGLIONATED PLEXI IN PATIENTS WITH ATRIAL FIBRILLATION

**Short Title:** CT Guided Ablation of Ganglionated Plexi

**Study Description:** Single-arm prospective study to evaluate the role of high frequency stimulation (HFS) and computed tomography (CT) guided mapping and ablation of ganglionated plexi (GP) in patients with atrial fibrillation.

**Objectives:** Primary:

Secondary:

To assess the effects of GP ablation on local HFS response and global vagal stimulation in order to characterize the neural pathways connecting GPs

**Primary Endpoint:** The primary outcome of interest will be the successful identification of GP signals by high frequency stimulation and anatomic correlation between these points and CT identified epicardial adipose tissue within 3 pixels ( $0.625 \times 3 = 1.875$ mm).

**Secondary Endpoints:**

[figure not shown]
- Elimination of local of HFS response following GP ablation
- Elimination of global vagal response to non-invasive ear stimulation
- Characterization of amplitude, duration, and fractionation of signals at sites with HFS responses and successful HFS elimination

**Study Population:** 19 patients with atrial fibrillation undergoing catheter ablation of atrial fibrillation

**Description of Sites/Facilities** All ablation procedures will be performed at the Hospital of the University of Pennsylvania.

### 1.3 Schema

## 2 INTRODUCTION AND RATIONALE

The heart has a complex network of autonomic innervation with the majority of input occurring at a series of ganglionated plexi. These ganglionated plexi are found in the epicardial adipose tissue around the base of the heart and interruption of these regions, most commonly through endocardial ablation, has been a potential treatment for multiple cardiac arrhythmias. This approach has become an accepted strategy for treating atrial fibrillation but may also be of value for vasovagal syncope, sinus node dysfunction, and heart block. Identification of the ganglionated plexi is challenging and multiple techniques have been utilized. We anticipate that using standard cardiac computed tomography (CT) to identify epicardial adipose tissue can provide a safe, non-invasive option to locate these regions and guide appropriate intervention. We also anticipate that a consistent network of innervation between the GPs will be identifiable with distinct innervation of the sinus and AV nodes.

### 2.1 Study Rationale

Despite progress made in treating atrial fibrillation with catheter ablation, outcomes remain suboptimal with pulmonary vein isolation alone. Ablation of ganglionated plexi has been shown to be beneficial in patients with atrial fibrillation although optimal strategies of localization of these regions have yet to be determined. We aim to develop a novel strategy of CT guided ganglionated plexi localization to guide ablation in patients with atrial fibrillation. We also aim to clarify the network of innervation between GP to clarify the optimal ablation strategy.

### 2.2 Background

Autonomic cardiac innervation arises from the brainstem and travels to the heart via the cervical and thoracic stellate ganglion (sympathetic system) and the vagus nerve (parasympathetic system). The two systems combine to innervate the heart in a dense network of post-ganglionic axons called the ganglionated plexi (Hou Y, et al). These ganglionated plexi are located at the base of the heart in the epicardial adipose tissue (Goudis CA, et al; Armour JA, et al).

With direct visualization of the epicardial adipose tissue at the time of cardiac surgery, autonomic modulation with injection of botulinum toxin has been shown to reduce short and long term burden of atrial fibrillation (Romanov A et al; Waldron et al). Several techniques have been proposed to identify the ganglionated plexi at the time of endocardial procedures. Anatomic approaches have been utilized targeting classical regions of autonomic innervation, although this procedure has several limitations including individual anatomic

variation. In addition, high frequency stimulation mapping to identify local vagal responses has been used (Kim MY, et al; Hu F, et al). This technique is limited by the need for general anesthesia and the duration of time required to map the entire atrium, which is especially relevant for non-atrial fibrillation ablation procedures where such mapping would not otherwise be required. More recently, techniques to evaluate local electrograms have been developed based on the principle that fractionated electrical activity may be noted in the endocardium beneath ganglionated plexi due to the inter-myocardial nerve fibers that interrupt normal myocardial-to-myocardial conduction (Pachon M JC, et al; Lellouche N, et al).

We have recently shown that there is an association between left atrial epicardial adipose tissue identified by CT imaging and electrogram fractionation (Zghaib T, et al). This association is consistent with other descriptions of local electrograms at the site of successful ablation of ganglionated plexi. Given the routine nature of pre-procedure imaging, which is frequently performed prior to atrial fibrillation ablation to clarify relevant anatomy, and the ability to identify this epicardial adipose tissue, we anticipate CT can provide a safe, non-invasive option to locate these regions and guide appropriate intervention. Ablation targeting ganglionated plexi have been used to treat atrial fibrillation as well as vasovagal syncope, sinus node dysfunction, and heart block. A simple and reliable method of identifying ablation target could improve the safety and efficacy of these procedures.

Update to 1/23/24 version: Although tragus stimulation has been frequently utilized, there is evidence to suggest more robust vagus nerve innervation in the region of the cymba concha (Frangos et al 2015; Rong et al 2012; Courties et al 2022). For this reason, electrodes positioned in this area may have more consistent physiologic effects related to vagus nerve stimulation.

### **2.2.1 Clinical Adverse Event Profile**

Potential complications of catheter ablation of atrial fibrillation include bleeding, vascular injury, cardiac perforation, atrioesophageal fistula formation, phrenic nerve injury, bradycardia, arrhythmia induction, myocardial infarction, and stroke. These complications are related to the insertion of catheters from the femoral veins into the heart and across the intra-atrial septum to the left atrium as well as the delivery of radiofrequency energy in the left atrium. We do not anticipate the mapping portion of the procedure, which will be performed with a standard ablation catheter, to confer significant additional risk. The most likely increased risk from high frequency stimulation is the induction of atrial fibrillation, which is common as part of routine ablation procedures and does not pose significant risk. We do not anticipate these risks to be significantly modified by the additional ablation targeting ganglionated plexi, which are located in regions frequently targeted in ablation of atrial fibrillation and atypical atrial flutters.

## **2.3 Risk/Benefit Assessment**

### **2.3.1 Known Potential Risks**

As discussed above, potential risks of ablation of ganglionated plexi include the risk factors associated with catheter ablation for atrial fibrillation as discussed above. An additional theoretical risk includes increased sinus rates following vagal denervation, which has been described as transient in the literature and not seen in our own experience. Potential risks of ear stimulation include local discomfort or skin irritation/burns. Potential risks of high frequency stimulation include pain, which will not be perceived given the use of general anesthesia, and the induction of atrial fibrillation, which routinely occurs during atrial fibrillation ablations.

### **2.3.2 Known Potential Benefits**

Potential benefits include the reduction in burden of atrial fibrillation by eliminating vagal triggers for atrial fibrillation. In addition, societal benefits include the development of procedural techniques that may improve treatment of atrial fibrillation, vasovagal syncope, and other conditions.

### **2.3.3 Assessment of Potential Risks and Benefits**

The risks of participating in the study are not significant beyond the risks associated with routine clinical care (including pre-procedural CT imaging, atrial mapping and ablation). Therefore, the potential benefits to the individual subject and to society outweigh the risks of participating in the study.

### 3 STUDY OBJECTIVES AND ENDPOINTS

OBJECTIVES	ENDPOINTS	JUSTIFICATION FOR ENDPOINTS
Primary		
	
 
Successful identification of GP signals by high frequency stimulation and anatomic correlation between these points and CT identified epicardial adipose tissue within 3 pixels (0.625x3=1.875mm).
 
	This correlation will allow us to determine the ability of pre-procedural CT imaging to predict GP location.
Secondary		
To assess the effects of GP ablation on local HFS response and global vagal stimulation in order to characterize the neural pathways connecting GPs	
 
Elimination of local of HFS response following GP ablation
 
Elimination of global vagal response to non-invasive ear stimulation
 
	
	
 
Amplitude, duration, and fractionation of signals at sites with HFS responses and successful HFS elimination
 
	

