### **4.2 Scientific Rationale for Study Design**

This study is designed to characterize the association between CT identified epicardial adipose tissue and HFS mapping identified GP sites in the right and left atrium. Given the evidence that GP ablation can be beneficial for patients undergoing catheter ablation for atrial fibrillation, all patients will undergo GP ablation following mapping in addition to standard pulmonary vein isolation. The hierarchical relationship within the network of cardiac GPs is unknown as is the optimal order of GP ablation. Given equipoise in the order of GP ablation, we will equally allocate the site of initial ablation between the 8 major GP ablation locations.

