## STUDY INTERVENTION

### 4.8 Study Intervention(s) Administration

#### 4.8.1 *Study Intervention Description*

All patients will have GP mapping performed using the Nicolet (Natus) Cortical Stimulator (see attached) with 12V output at 20Hz frequency with 10ms pulse duration with at least 3grams of contact force. Stimulation will be provided for up to 10 seconds or until vagal response is noted (>2s ventricular asystole, AV block, or R-R interval increase by at least 50%). Natus stimulator had FDA clearance (K072964) for cortical stimulation. Prior to ablation, baseline ear vagus nerve stimulation will be performed via stimulation of bilateral cyma concha to document response using Parasym tragal stimulator (IDE information attached). Ablation of mapped GPs will be performed using standard ablation catheter with routine approaches to ablation energy delivery and monitoring (see below flowchart). Following ablation of each GP, local HFS will be repeated in all GP regions and ear vagus nerve stimulation will be repeated via bilateral cyma concha. After all GP are ablated, all patients be given IV atropine (0.04mg/kg max: 4mg) to assess global vagal tone. Following this, patients will undergo pulmonary vein isolation using standard equipment and techniques.

Devices will be obtained from the manufacturer (Natus and Parasym respectively) and will be stored in a secured laboratory space. No particular temperature or climate requirements are present for either device. All devices will be labeled according to the manufacturer guidance and will be returned to the manufacturer in the event of any device failure. Devices will be stored and managed in compliance with OCR guidelines.

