## 7 STATISTICAL CONSIDERATIONS

### 7.1 Statistical Hypotheses

- Primary Efficacy Endpoint(s): We anticipate anatomic correlation between CT identified epicardial adipose tissue within 3 pixels ( $0.625 \times 3 = 1.875\text{mm}$ ) of an endocardial mapping point where HFS confirmed a vagal response consistent with ganglionated plexus innervation.
- Secondary Efficacy Endpoint(s): Acute procedural success defined by elimination of ear vagus nerve stimulation response will be achievable in all patients.

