#### 7.2.2 *Analysis of the Primary Efficacy Endpoint(s)*

- Anatomic correlation between CT and GP mapping will be defined based on review of electroanatomic maps from the ablation procedure merged with segmented pre-procedural CT images.

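### The primary endpoint looks for CT fat only at HFS-positive points, so it can show concordance but not the claimed prediction of GP location

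*Combined protocol and SAP*

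**What the plan says.** The primary endpoint, given in the synopsis and in section 3, has two parts: GP signals are found by HFS, and those points are then related to CT-identified epicardial fat with a tolerance of 3 pixels (1.875 mm). The hypothesis in section 7.1 likewise expects fat within that distance "of an endocardial mapping point where HFS confirmed a vagal response consistent with ganglionated plexus innervation". Section 7.2.2 says only that the correlation is defined from "review of electroanatomic maps from the ablation procedure merged with segmented pre-procedural CT images". It names no statistic, comparison group or coverage measure.

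The stated purposes are wider. Section 3 justifies the endpoint with "This correlation will allow us to determine the ability of pre-procedural CT imaging to predict GP location". Section 4.2 says: "This study is designed to characterize the association between CT identified epicardial adipose tissue and HFS mapping identified GP sites". Section 2.1 says: "We aim to develop a novel strategy of CT guided ganglionated plexi localization to guide ablation in patients with atrial fibrillation". Section 2.2 adds: "we anticipate CT can provide a safe, non-invasive option to locate these regions and guide appropriate intervention".

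On mapping, section 4.8.1 says: "Stimulation will be provided for up to 10 seconds or until vagal response is noted". Sites without a response are therefore a possible outcome, but no use of them is specified.

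**The concern.** The endpoint estimates how often fat is nearby, given a vagal response. Prediction runs the other way: given fat on CT, how likely is a response? The first figure does not yield the second without the rate of fat proximity at sites that did not respond, or at least the share of the surface that lies near fat. The association aim in section 4.2 needs the same second group.

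The problem is one-sided. A low concordance would be informative, because CT fat would then be missing HFS-positive sites. A high one is hard to read. Section 2.2 already says: "These ganglionated plexi are located at the base of the heart in the epicardial adipose tissue". A high value is therefore largely what the background leads one to expect. For a tool meant to locate GPs and guide ablation, the open question is how selectively fat marks the responding sites, and the endpoint does not measure that.

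At stake is the study's conclusion, not care within the trial, where the GPs that are ablated are those found by mapping. A favourable result could be read as support for CT fat as an ablation guide even if most fat-adjacent stimulated sites do not respond.

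**Working it through.** **The plan's own figure.** 3 × 0.625 = 1.875 mm, which reproduces. The sample size of 19 comes with no rate, effect size or power that could be checked.

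**Inputs.** The documents give none of the rates below, so all are assumptions:
- s = share of HFS-positive points with fat within 1.875 mm (what the endpoint gives), set at 0.80
- q = the same share at HFS-negative points (not planned), varied from 0.10 to 0.80
- π = share of tested points that are HFS-positive, 0.20, with a range of 0.10 to 0.30

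**Formulas.** Positive predictive value (PPV) = πs / [πs + (1 − π)q]. Odds ratio = [s/(1 − s)] / [q/(1 − q)].

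Example with q = 0.40 and π = 0.20: PPV = 0.16 / (0.16 + 0.32) = 0.33; odds ratio = 4 / 0.667 = 6.0.

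| q | PPV, π = 0.20 | PPV, π = 0.10 to 0.30 | Odds ratio |
|---|---|---|---|
| 0.10 | 67% | 47–77% | 36 |
| 0.40 | 33% | 18–46% | 6.0 |
| 0.60 | 25% | 13–36% | 2.7 |
| 0.80 | 20% | 10–30% | 1.0 |

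Every row has the same endpoint result, 80%. In the last row PPV equals π, so CT fat carries no information.

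**PPV also depends on sampling.** Take 8 HFS-positive sites per patient, n HFS-negative sites and q = 0.40. PPV = 6.4 / (6.4 + 0.4n), which is 67%, 50% and 33% for n = 8, 16 and 32. Specificity (60%) and the odds ratio (6.0) do not move.

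**Could 80% arise with no association?** Assume 19 × 8 = 152 pooled, independent points. Since 0.80 × 152 = 121.6, at least 122 must be near fat. If proximity is unrelated to response and coverage is c, P(X ≥ 122) with X ~ Bin(152, c) is about 8 × 10⁻⁸ at c = 0.60, 0.3% at 0.70 and 52% at 0.80. Clustering within patients would widen the distribution, so the two small values are too small.

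**Can 19 patients support the comparison?** Simulation with 2,000 trials per setting: 8 HFS-positive and 8 or 32 HFS-negative sites per patient; logit random intercept SD 0.6 or 1.2 (intracluster correlation about 0.1 or 0.3); random HFS effect SD 0 or 1.0; marginal rates 0.80 versus q; log odds ratio with 0.5 added to each cell. The interval is a delete-one-patient jackknife with t on 18 df.

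| q | Trials with lower 95% limit of the odds ratio above 1 |
|---|---|
| 0.40 | about 100% |
| 0.60 | 85–100% |
| 0.70 | 35–71% |
| 0.80 (no association; nominal 2.5%) | 1.8–2.9% |

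Separate codings of the same model agree closely; the lowest figure at q = 0.70 was 30%. In a single run, an uncorrected patient bootstrap gave 3.3–5.2% at q = 0.80, which is why a small-sample correction is needed. The 95% half-width for the difference in fat-proximity shares is about 7 to 13 percentage points.

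**The case against.** The strongest reply is that the analysis is undefined rather than wrong. Correlation and association are loose terms, section 7.2.2 names no denominator, and nothing there excludes non-responding points from the merged maps. The primary objective is blank in the text available, and the schema and the flowchart for section 4.8.1 are not shown. This is also a single-center observational study of 19 patients with no success threshold, so an overclaim is a forecast. A high value would not be trivial either: it would show that segmented, merged CT places fat within 1.875 mm of a responding endocardial site. Finally, no association at 80% concordance needs coverage near 80%, and every rate used here is assumed.

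Parts of this stand. The sizes are illustrations, the documents do not say what coverage is plausible, and the blank cell and missing figures are not held against the plan. Registration accuracy is a real product of the endpoint.

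The main point survives. The endpoint and the hypothesis both tie the fat measurement to HFS-positive points, section 3 explicitly claims prediction, and no legible text supplies a comparator. An exploratory study may report concordance alone, but it should then call it that. Rewording would largely settle the claim in section 3, although the association aim in section 4.2 would still need a reference rate.

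**Conclusion.** The concern holds and should be fixed. As written, the primary endpoint supports a statement of concordance (sensitivity of CT fat for HFS-positive sites). It does not support the stated claim of prediction, nor by itself the association aim. This rests on the wording of sections 3, 7.1 and 7.2.2 and does not depend on any assumed rate.

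The size does depend on assumptions. At 80% concordance with 20% of points HFS-positive, the same result fits a PPV anywhere from 67% down to 20%, as fat proximity at HFS-negative points goes from 10% to 80%. Complete absence of association is the extreme case and needs coverage near 80%; weak selectivity needs much less.

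**What to change.** In sections 3, 7.1 and 7.2.2:

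1. Record the location and result of every stimulated site, responders and non-responders, and classify each by CT fat within 1.875 mm on the same merged maps.
2. Report the fat-proximity share in HFS-positive and in HFS-negative sites, specificity, PPV and the odds ratio. Give 95% intervals that account for clustering by patient, with a small-sample correction for 19 clusters (for example a delete-one-patient jackknife or bias-corrected GEE, with t on 18 df). Describe an odds-ratio interval above 1 as association only, not prediction.
3. State which regions were stimulated and limit specificity and PPV to them. Note that PPV depends on how many negative sites are sampled. Call non-responders HFS-negative, not GP-absent.
4. If fat-free areas are not sampled, compare concordance with the fat coverage of the stimulated or mapped surface at the same tolerance, and restate the justification in section 3 as concordance.

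The cost is protocol wording, tagging of each stimulated site and some extra analysis, with no extra patients. Tagging should be set up prospectively, because negative results may not be recoverable later. The headline may be less flattering, and a difference of about 10 points (80% versus 70%) may not be resolved with 19 patients. Wider sampling of fat-free areas would add mapping time, which section 2.2 already names as a limitation of HFS; the coverage comparison in item 4 avoids that.

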## **4 STUDY PLAN**

### **4.1 Study Design**

This is an observational, single-center study evaluating feasibility and efficacy of CT and high frequency stimulation guided GP mapping and ablation in patients with AF undergoing catheter ablation with pulmonary vein isolation.

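### The primary agreement rate uses only HFS-positive points, and no rule keeps HFS site choice independent of CT, so by itself it cannot show that CT fat predicts GP location

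*Combined protocol and SAP*

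**What the plan says.** The synopsis (section 1.1) describes the study as one of "high frequency stimulation (HFS) and computed tomography (CT) guided mapping and ablation of ganglionated plexi (GP"), and section 4.1 repeats the idea, describing a study "evaluating feasibility and efficacy of CT and high frequency stimulation guided GP mapping and ablation". In both places CT is attached to the mapping, not only to the ablation.

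Section 3 gives the primary endpoint as "Successful identification of GP signals by high frequency stimulation and anatomic correlation between these points and CT identified epicardial adipose tissue within 3 pixels", with the tolerance worked out as "0.625x3=1.875mm". The justification beside it reads "This correlation will allow us to determine the ability of pre-procedural CT imaging to predict GP location". Section 7.1 expects such a correlation but sets no target rate, no chance level and no comparison with points away from fat.

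Section 4.8.1 gives the stimulator settings, the minimum contact force and the criteria for a vagal response. It does not say where baseline HFS is delivered, how densely, whether sites away from fat are tested, or whether the operator can see the fat segmentation. Section 7.2.2 bases agreement on "review of electroanatomic maps from the ablation procedure merged with segmented pre-procedural CT images". It does not say that segmentation and registration are finished before HFS results are known, and it gives no role to HFS-negative points. The contents list has an entry 4.9 on randomization and blinding, but section 4.9 in the body is about compliance.

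The flowchart cited in section 4.8.1, the schema and the text of the primary objective are not available in the copy reviewed. They are not counted against the plan.

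**The concern.** CT is the test under evaluation and HFS is the reference. If the test steers where the reference is applied, agreement between them partly reflects the steering. A point can be HFS-positive only if it was stimulated, so when stimulation is concentrated near fat, the positive points will be near fat whether or not fat marks ganglionated plexi.

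The same difficulty arises without any CT steering. If baseline HFS is confined to classical GP regions, and those regions are mostly covered by fat, agreement will be high by geometry alone. An endpoint built only from positive points has nothing to set that against.

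At stake is the main conclusion of the study. A high agreement rate would be reported as evidence that pre-procedural CT locates the plexi, and it could arise with no such ability. If negative points are not stored during the procedure, the comparison cannot be rebuilt afterwards.

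**Working it through.** **The plan's own figure.** Section 3: 3 pixels × 0.625 mm = 1.875 mm. This reproduces. The sample size of 19 (section 1.1) comes with no effect size, power or null rate, so there is nothing further to reproduce.

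**Notation.** Let f be the share of stimulated points within 1.875 mm of CT fat, r1 the HFS response rate near fat, and r0 the rate away from fat. The documents give none of these; every value below is an assumption.

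- Near-fat share among HFS-positive points (the primary endpoint): f·r1 / [f·r1 + (1 − f)·r0].
- Near-fat share among HFS-negative points: f·(1 − r1) / [f·(1 − r1) + (1 − f)·(1 − r0)].

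**No association (r1 = r0).** The response rate cancels and both shares equal f.

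**A real association.** Take r1 = 0.30 and r0 = 0.125. The odds ratio is (0.30/0.70) / (0.125/0.875) = 3.0. At f = 0.5, the positive share is 0.150/(0.150 + 0.0625) = 71% and the negative share is 0.350/(0.350 + 0.4375) = 44%.

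| f (assumed) | Agreement, no association | Agreement, odds ratio 3 | Near-fat share of negatives, odds ratio 3 |
|---|---|---|---|
| 0.3 | 30% | 51% | 26% |
| 0.5 | 50% | 71% | 44% |
| 0.7 | 70% | 85% | 65% |
| 0.9 | 90% | 96% | 88% |
| 1.0 | 100% | 100% | 100% |

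Two things follow. First, an observed agreement of about 70% fits a threefold odds ratio at f = 0.5 and no association at f = 0.7, so the endpoint cannot tell them apart. Second, the contrast between positive and negative points can: with no association the two columns coincide, and with the assumed association the odds ratio is 3 at every f below 1 (at f = 0.9, (0.27/0.0125) / (0.63/0.0875) = 21.6/7.2 = 3). At f = 1 there is no contrast left, which is why some sites away from the expected regions are needed.

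**Illustration with 19 units.** Suppose, for illustration only, one independent yes/no result per patient, tested against a 50% chance level. Fifteen or more of 19 would reject it: exact one-sided p = 0.0096, doubled 0.0192, below the two-sided 0.05 of section 7.2.1. With no true association, 15 or more occurs with probability 0.28 if f = 0.7 and 0.96 if f = 0.9. The plan names no such test; the example shows only how strongly the answer depends on f.

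**The case against.** The strongest reply is that CT guidance may be a label for the goal and not a sampling rule. Section 2.1 speaks of developing a CT-guided strategy. Section 4.8.1 describes mapping by HFS alone, section 4.2 refers to GP sites identified by HFS mapping, and section 7.1 starts from a point with a confirmed response and then relates it to fat. Section 7.2.2 fits a comparison made after the procedure. Section 4.2 also names 8 major GP locations for the order of ablation, and section 4.8.1 repeats HFS across all GP regions, which suggests predefined regions. The response criteria are objective rhythm changes, so labelling a point as positive is not the weak step.

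Much of this stands. A reader might infer that operators do choose HFS sites from the CT, or that the merged maps are read with HFS results in view. The documents support neither: they do not say how baseline sites are chosen, and section 7.2.2 is silent on what the reader sees. The missing flowchart or schema might settle the order of work. It is also fair that the percentages above are assumptions fed through an identity; they show the mechanism and do not measure bias in this study.

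What does not stand is the inference that predefined regions remove the problem. Section 2.2 places the plexi within epicardial fat, so region-based sampling may itself give a high f. Section 2.2 also counts the time needed to map a whole atrium among the limits of HFS, which is a practical reason to sample selectively.

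**Conclusion.** The concern holds as a limit on what the primary result can conclude. The visible plan permits CT-informed choice of HFS sites and specifies no analysis of negative points. With no association, expected agreement equals f; f is unknown, and any value from about 30% to 90% is an assumption. The agreement rate alone therefore cannot show that CT predicts GP location, even if sites were chosen by region and not from the CT.

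It does not follow that CT-directed sampling occurs, that the map review is unmasked in practice, or that this study's result will be inflated by any particular amount. This should be corrected before further baseline mapping, because negative points that are not stored cannot be recovered.

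**What to change.** In sections 4.8.1 and 7.2.2:

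1. Complete and lock the CT fat segmentation before the procedure.
2. Choose baseline HFS sites without reference to that segmentation, keep the overlay hidden until the last baseline HFS point is stored, and include some sites away from the expected GP regions.
3. Store every stimulated point, positive and negative.
4. Fix the registration of map to CT on anatomical landmarks before HFS labels are added.
5. Make the primary analysis a comparison of the near-fat proportion between HFS-positive and HFS-negative points, for example an odds ratio, or sensitivity and specificity, allowing for clustering by patient.

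If mapping is already done independently of the CT, item 2 needs little more than a sentence saying so and the added sites; item 5 is needed either way. A dense fixed grid over both atria is not required: given the time burden noted in section 2.2, that is a debatable trade-off.

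The cost is somewhat longer baseline mapping and slightly more data handling. No extra patients, imaging or staff are needed.
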